8.1. Efficacy Assessments

8.1.1. Hemophilic Bleeding Episodes and Treatment

An eDiary, a handheld device, will be provided to all participants on Visit 1. The participants are required to enter any occurrence of hemophilic bleeding episodes (including date, time, location and etiology) and any exogenous FVIII replacement (including date, time, reason, and dose) required to treat the bleeds in the eDiary.

If bleeding episodes or treatments are not entered during the appropriate time window in the eDiary, participants should communicate all bleeds and all relevant infusion data not entered into the eDiary to the investigator (or appropriate site staff member), and data should be entered by the investigator (or appropriate site staff member) according to the process in place with appropriate source documentation in the participant's medical record. Non-FVIII treatments or procedures to treat bleeds, will be entered by the investigator (or appropriate site staff member) according to the process in place.

The site staff should counsel participants regarding late eDiary entries and emphasize the importance of being compliant with expected eDiary entries (eg, it helps monitor the participant's condition throughout the study) and of reporting all bleeds and all relevant infusion data to the site staff on a contemporaneous basis.

During the site visits, the investigator (or qualified designee) will review the eDiary with participants. Bleeding episodes and any related treatments will be reviewed to ensure consistency between the medical record and/or eDiary (and/or CRF).

In the event that a participant may have to resume FVIII prophylaxis treatment, prophylaxis FVIII infusion data will not have to be reported on the eDiary (or conveyed to the study site staff on a contemporaneous basis) after Week 78 (Visit 14). Bleeds and non-prophylactic infusions (eg, on-demand and preventative) should continue to be reported throughout the course of the study. Prescribed FVIII product information will continue to be captured (eg, change in regimen), by the site staff, according to the process in place.

Bleeding episodes requiring treatment with FVIII product (as recommended in the World Federation of Hemophilia guidelines)³⁹ will count toward the determination of bleeding episode frequency and the eDiary and/or medical record will serve as the source document for bleeding episodes. Definitions of bleeds are in [Appendix 7](#).

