	
compared with prior FVIII prophylaxis replacement regimen:
 
 • Annualized FVIII consumption. • Treated ABR of specific type: 
 ◦ by cause (spontaneous or traumatic) ◦ by location (in joints, in target joints, or in soft tissue). • Total ABR by cause and by location. • Percentage of participants without bleeds. 
The following secondary parameters will be assessed by visit after PF-07055480 infusion:
 
 • FVIII activity level. • Change from baseline in joint health as measured by the Hemophilia Joint Health Score (HJHS) instrument. • Change from baseline in the following PRO endpoints: 
 ◦ Haemophilia Quality of Life Questionnaire for Adults (Haem-A-QoL) ◦ Haemophilia Activities List (HAL)

 • Estimate the durability of efficacy up to 5 years after PF-07055480 infusion. 	
The following parameters will be analyzed yearly or by visit as appropriate:
 
 • Treated ABR. • FVIII activity level. • AIR of exogenous FVIII. • Annualized FVIII consumption. • Treated ABR of specific type: 
 ◦ by cause (spontaneous or traumatic).

Objectives	Endpoints
	
 ○ by location (in joint, in target joints, or in soft tissue). ● Total ABR. ● Total ABR by cause and by location. ● Percentage of participants without bleeds. ● Change from baseline in joint health as measured by the HJHS instrument. ● Change from baseline in PRO endpoints: Haem-A-QoL and HAL. 
In addition, Treated ABR, Total ABR, and AIR will be analyzed throughout the 5-year study period.

Secondary Safety Objective	Secondary Safety Endpoints

 ● To estimate the safety and tolerability of PF-07055480, including immunogenicity, for the study duration of 5 years after PF-07055480 infusion. 	
 ● Incidence and severity of adverse events (AEs). ● Events of special interest (such as hypersensitivity reactions, clinically reported thrombotic events, and malignancy). ● Immunogenicity: 
 ○ Antibodies against adeno associated viral vector, serotype 6 (AAV6) capsid protein (neutralizing antibodies [nAbs] and anti-drug antibodies [ADAs]). ○ T-cell responses against AAV6 capsid and against the transgene. ○ FVIII inhibitors.
Tertiary/Exploratory	

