Cumulative follow up through 5 years postinfusion	Day 78 to End of the study

For participants with incomplete data for the entire yearly time period, including participants who discontinued, all data during the specified period will be annualized and summarized utilizing the number of days of follow-up during the given time period (i.e., observation period). Total ABR for each participant will be calculated as below:

Total ABR =

$$\frac{(\text{Number of treated and untreated bleeding episodes during the given time period}) \times 365.25}{(\text{Number of days of follow-up in the given time period})}$$

Data before Week 12 postinfusion are excluded to account for the potential differences in participants' pharmacokinetics postinfusion. As a result, the denominator in the above calculation for the Month 15 and cumulative follow-up intervals will be [the last date in the given time period – (Date of PF-07055480 infusion) – 77 days +1].

For the primary endpoint assessment of Total ABR from Week 12 through at least 15 months (up to data cutoff), the number of bleeds post resumption of prophylaxis regimen or study discontinuation will be excluded. As a result, the denominator (i.e., number of days in the observation period) in the above Total ABR calculation will include days up to data cutoff, the day before resumption of prophylaxis regimen, or discontinuation date, whichever occurs earliest.

Total ABR during yearly intervals and cumulative follow-up intervals are considered as secondary endpoints. If the participant discontinues from study before the end of the prespecified observation period, the last date in the given observation period will be the date of study discontinuation. In addition, if FVIII prophylaxis regimen is resumed for a participant as defined in Protocol Section 6.5.1 then data collected on and after the date of prophylaxis resumption entered in the eCRF by the investigator will be excluded from the calculation of Total ABR by interval, which means the bleeding events will be excluded and the corresponding time period will be deducted as well.

Total ABR prior to PF-07055480 will be calculated using all treated and untreated bleeds documented during the lead-in study (C0371004) up to preinfusion of PF-07055480 and the respective number of days of follow-up within the lead-in study and preinfusion period using the same formula presented above.

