3.2.3. Annualized Infusion Rate (AIR) of Exogenous FVIII

AIR of exogenous FVIII replacement following PF-07055480 infusion from Week 12 [Day 78] through at least 15 months (up to data cutoff) after PF-07055480 infusion is considered as a secondary endpoint and will be compared with AIR during prior FVIII prophylaxis replacement regimen.

All infusions during the observation time period for any purpose (to treat bleeding, for preventive purpose, perioperative, or if FVIII prophylaxis regimen is resumed) will be included in the calculation of AIR. AIR data after PF-07055480 infusion will additionally be analyzed for the yearly intervals as well as cumulative follow-up intervals as separate secondary endpoints.

For participants with incomplete data for the entire yearly time period, including participants who discontinued prior to completing the study, all data during that period will be annualized and summarized utilizing the number of days of follow-up during the given time period. AIR for each participant will be calculated as below:

$$\text{AIR} = \frac{(\text{Number of infusions for any purpose during the given time period}) \times 365.25}{(\text{Number of days of follow-up in the given time period})}$$

Same as explained in [Section 3.1.1](#), the follow-up period will exclude the first 11 weeks (77 days). The denominator in the above calculation for postinfusion up to data cutoff, Month 15 interval and cumulative follow-up intervals will be [the last date in the given time period – (Date of PF-07055480 infusion) – 77 days +1]. If the participant discontinues from study before the end of the prespecified time period, the last date in the given time period will be the date of study discontinuation.

If a participant has to resume FVIII prophylaxis treatment, prophylaxis FVIII infusion data will not have to be reported on the eDiary (or conveyed to the study site staff on a contemporaneous basis) after Week 78 (Month 18). The eDiary will continue to collect bleeds and non-prophylactic infusions (e.g., on-demand and preventative) throughout the course of the study. The prophylaxis infusion data will be derived from the prescribed FVIII product information and included in the AIR calculation.

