6.1.1.2. Sensitivity/Supplementary Analyses

The following sensitivity analyses will be performed for Total ABR in the primary analysis without hypothesis testing unless specified:

- The same analysis model and summary as described above for the main analysis will be repeated on the Total ABR from Week 12 through data cutoff, using the ‘Dosed’ population regardless of the length of follow-up in preinfusion or postinfusion.
- Same analysis as described for the main analysis will be performed on the Total ABR from Week 12 through data cutoff, using the ‘Evaluable’ population if it is different from the ‘Dosed’ population.
- Two sensitivity analyses will be performed to include the bleeding data collected during only the latest 6 months and the first 6 months separately during the lead-in study up to preinfusion of PF-07055480 in order to support the robustness of the primary analysis results and confirm the absence of seasonal effect, using the

‘Efficacy’ population. In these sensitivity analyses, all the participants will have the same length (i.e., 6 months) of preinfusion observation period.

- Include only the data collected in the lead-in study (C0371004) (i.e., excluding the preinfusion data in C3731003) and the data postinfusion of PF-07055480 using the same analysis model as described above. This analysis will be conducted on the ‘Efficacy’ population.

Additional US-specific analyses are described in [Appendix 1.4](#).

Supplementary analyses (to be conducted on the ‘Efficacy’ population): Total ABR 15 months, Year 2, Year 3, Year 4, and Year 5 as defined in [Section 3.1.1](#), as well as Total ABR in cumulative follow-up intervals (i.e., from Week 12 [Day 78] through 2 years postinfusion, from Week 12 [Day 78] through 3 years postinfusion, etc.), will be compared separately to Total ABR of FVIII prophylaxis (pre-PF-07055480) using the same statistical method as for Total ABR as described in [Section 6.1.1.1](#) except that noninferiority test or superiority test won’t be performed. For analyses by yearly interval, participants who have discontinued from the study or resumed prophylaxis regimen prior to the start of a given yearly interval will be excluded.

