Appendix 1.4. Additional US-specific Analyses

Total ABR:

Supplementary analysis: Repeat the same analysis model and summary for the main analysis as described in [Section 6.1.1.1](#) on the Total ABR from Week 12 through data cutoff using the ‘Dosed’ population regardless of the length of follow-up preinfusion or postinfusion. In addition, the imputation rule per given event below in Table 10 will be applied.

Table 10. Imputation Rules for US-Specific Analysis of Total ABR

Event	Imputation Rule
Resumption of prophylaxis regimen	The Total ABR post prophylaxis resumption date through data cutoff will be imputed with 35.
Taking FVIII infusions post PF-07055480 infusion for a time period in a manner similar to prophylaxis regimen (Note: these events will be identified based on clinical review.)	The Total ABR during this period will be imputed with 35.

If a participant resumes prophylaxis regimen and then later discontinues from the study prior to data cutoff, his Total ABR post prophylaxis resumption data through data cutoff will be imputed with 35 (i.e., the imputation rule will be applied for the period from study discontinuation to data cutoff).

The corresponding supplementary estimand is the treatment effect of PF-07055480 compared to routine prophylaxis with respect to Total ABR (treated and untreated bleeds) after prior prophylaxis treatment is stopped following infusion, from Week 12 [Day 78] through data cutoff.

Table 11. Supplementary Estimand of Total ABR

Estimand Attribute	Description
Population	Male participants ≥ 18 years of age with moderately severe to severe hemophilia A (FVIII:C $\leq 1\%$), who have tested negative for anti-AAV6 nAb and have no medical history of FVIII inhibitor.
Variable	Total ABR (treated and untreated bleedings) from Week 12 [Day 78] through data cutoff post PF-07055480 infusion.
Intercurrent Event	
 • Data post prophylaxis resumption date through data cutoff will be imputed. • Data during a time period when the participant was taking FVIII infusion in a manner similar to prophylaxis regimen will be imputed. • Data after study discontinuation will not be imputed unless prophylaxis was resumed prior to discontinuation.

Estimand Attribute	Description

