Treated ABR by yearly interval (Month 15, Years 2-5)	
 Primary analysis: supplementary analysis Final analysis 	Efficacy / Dosed	
 Any data after the resumption of FVIII prophylaxis regimen (if necessary) will be excluded. Data after study discontinuation won't be imputed. Participants who have discontinued from the study or resumed prophylaxis regimen prior to the start of a given yearly interval will be excluded. 	Same as above for Total ABR (from Week 12 through at least 15 months [up to data cutoff] postinfusion of PF-07055480) but no hypothesis testing.
Treated ABR by cumulative follow-up interval	
 Primary analysis: supplementary analysis Final analysis 	Efficacy / Dosed	Same as above.	Same as above for Total ABR (from Week 12 through at least 15 months [up to data cutoff] postinfusion of PF-07055480) but no hypothesis testing.
FVIII activity level <1%, 1-5%, >5-<15%, 15-<40%, 40-<150%, >150% at Year 4, and Year 5 (using protocol-defined visit windowing)	Final analysis	Dosed	See imputation rules described in Section 3.2.5 .	Number (%) of participants
FVIII activity at Year 4 and Year 5	Final analysis	Dosed	Same as above.	Order statistics (consisting of minimum, percentiles at 10%,

Endpoint	Analysis Type	Population	Data Inclusion and Rules for Handling Intercurrent Events and Missing Data	Analysis
				25%, 50%, 75%, and 90%, and maximum).
AIR of exogenous FVIII by yearly interval (Month 15, Years 2-5)	
 Primary analysis: supplementary analysis Final analysis 	Efficacy / Dosed	No imputation for missing data.	Paired t-test.
AIR of exogenous FVIII by cumulative follow-up interval	
 Primary analysis: supplementary analysis Final analysis 	Efficacy / Dosed	No imputation for missing data.	Paired t-test.
Annualized FVIII consumption by yearly interval (Month 15, Years 2-5)	
 Primary analysis: supplementary analysis Final analysis 	Efficacy / Dosed	No imputation for missing data.	Paired t-test.
Annualized FVIII consumption by cumulative follow-up interval	
 Primary analysis: supplementary analysis Final analysis 	Efficacy / Dosed	No imputation for missing data.	Paired t-test.

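### The yearly ABR tables for the 5-year durability objective describe only participants not on prophylaxis, so they can understate waning when failures resume promptly

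*SAP*

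**What the plan says.** SAP 2.2 lists a secondary objective, "Estimate the durability of efficacy up to 5 years after PF-07055480 infusion", with Treated and Total ABR analysed by year among its endpoints.

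For yearly Total ABR, SAP 6.1.1.2 states that participants who discontinued or "resumed prophylaxis regimen prior to the start of a given yearly interval will be excluded". Appendix 2 gives the same rule for Treated ABR and carries it to the other yearly ABR rows by a 'same as above' entry, for both the primary-analysis supplementary tables and the final analysis. When resumption falls inside an interval, SAP 3.1.1 says that "the bleeding events will be excluded and the corresponding time period will be deducted as well".

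Two other durability endpoints keep resumers in. For AIR, SAP 3.2.3 says that infusions for any purpose, "or if FVIII prophylaxis regimen is resumed) will be included in the calculation of AIR". For FVIII activity by visit, SAP 3.2.5 assigns 0.9% after resumption.

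The SAP also has a rule that treats resumption as failure on the bleed scale. Appendix 1.4, Table 10: "The Total ABR post prophylaxis resumption date through data cutoff will be imputed with 35". It is planned for the whole period from Week 12 to data cutoff, not by year.

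**The concern.** Protocol 6.5.1 lets a participant resume prophylaxis when gene therapy is not efficacious, defined by FVIII activity of 1% or less or by repeated spontaneous bleeds. Resumption is therefore largely a marker of failure. Removing resumers from every later interval filters the analysis set on the outcome being measured, and the set shrinks from year to year. Each yearly table still gives a model-based difference from preinfusion prophylaxis with a 95% CI, for a group whose composition keeps changing. SAP 2.2.3 declares no additional estimands, so this conditioning is not stated anywhere as a target of estimation.

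At stake is how the 5-year bleed result reads. A row of similar yearly ABRs could be taken as sustained effect in everyone dosed, when it describes those who have not yet gone back to prophylaxis.

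**Working it through.** The plan gives no expected yearly ABR, so there is no figure of its own to reproduce here. Its power statement (at least 95%) concerns the primary test, which this point does not touch.

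**Inputs from the documents.** Total ABR r = 2 bleeds/year after gene therapy and 5 on prior prophylaxis (Protocol 9.2); imputed value 35 (SAP Table 10); interval limits from SAP 3.1.1, with Year 5 taken to Day 1825; 70 participants (Protocol 9.2).

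**Assumed, not in the documents.** Loss of effect at 10% per year from Day 78 (range 5–20%); lag L = 90 days from loss to resumption (range 30–90); f = 5 bleeds/year during the lag (range 5–12). Everyone who loses effect resumes, responders stay at r, and nobody discontinues.

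**Step 1: SAP rule.** λ = −ln 0.9 = 0.1054 per year. The share not yet resumed at day t is S(t) = exp[−λ(t − 77 − L)/365.25]. Of these, the share already without effect is 1 − 0.9^(90/365.25) = 0.0256, whatever t is. From Year 2 on,

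yearly ABR = r + (f − r) × 0.0256 = 2 + 3 × 0.0256 = 2.08.

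Calendar time drops out of the formula, so the curve is flat.

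**Step 2: number left.** At the start of Year 5, S(1460) = exp(−0.1054 × 1293/365.25) = 0.689, and 70 × 0.689 = 48.2. About 31% have been removed.

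**Step 3: keep resumers in.** Let q be the mean of S(t) over an interval. ABR = q × (SAP-rule ABR) + (1 − q) × v, with v = 5 or 35. For Year 5, q = 0.6537:

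- v = 5: 0.6537 × 2.077 + 0.3463 × 5 = 3.09
- v = 35: 0.6537 × 2.077 + 0.3463 × 35 = 13.48

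| Interval | Entering (of 70) | q | SAP rule | Kept at 5 | Kept at 35 |
|---|---|---|---|---|---|
| Month 15 | 70.0 | 0.969 | 2.07 | 2.16 | 3.08 |
| Year 2 | 64.4 | 0.885 | 2.08 | 2.41 | 5.87 |
| Year 3 | 59.5 | 0.807 | 2.08 | 2.64 | 8.44 |
| Year 4 | 53.6 | 0.726 | 2.08 | 2.88 | 11.09 |
| Year 5 | 48.2 | 0.654 | 2.08 | 3.09 | 13.48 |

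A simulation on the same assumptions agrees (SAP rule 2.07–2.09; 13.45 in Year 5 at 35).

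**Step 4: range.** Over the assumed ranges, Year 5 ABR is 2.0–2.5 under the SAP rule, 2.6–4.0 with resumers at 5, and 8.2–22.2 at 35. Between 17% and 56% are removed before Year 5. The SAP-rule figure never moves by more than 0.1 between Month 15 and Year 5.

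**Step 5: when waning does show.**

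- Half of those who lose effect never resume and bleed at 8/year, as do the others during their lag. In Year 5 the shares are 0.637 with effect, 0.1815 without effect and not resuming, and 0.0084 in the lag. ABR = (2 × 0.637 + 8 × 0.1815 + 8 × 0.0084)/0.8269 = 3.38, up from 2.23 at Month 15.
- Every responder's own rate rises 10% per interval, with resumption unrelated to that rate. Year 5: 2 × 1.1⁴ = 2.93, and 2.93 × 0.9744 + 5 × 0.0256 = 2.98, up from 2.07.
- The same 10% rise, but participants with higher rates resume sooner (simulated with between-participant variation). Reported yearly ABR stays at 1.90–1.94 while the mean of everyone's own rate goes from 2.0 to 2.9.

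The masking therefore depends on how closely and how quickly resumption follows loss of effect.

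**The case against.** The strongest defence is that the rule follows the chosen strategy. The primary estimand also excludes data after resumption, and a participant already back on prophylaxis has no eligible time in the interval. That is consistent. But over the whole period from Week 12 to cutoff he still contributes his time before resumption, whereas in each later yearly table he contributes nothing.

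The SAP also plans outputs that reveal failures: percent resumed and time to resumption by yearly and cumulative interval (6.2.3.2), a participant-level failure listing (6.1.1.3), n in each ABR table, cumulative ABR from Day 78, AIR and FVIII by visit. This stands as partial mitigation. None of these changes the yearly ABR estimate or its comparison with prophylaxis, and cumulative ABR drops time after resumption too.

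A reader might infer more than the documents support:

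- **That the yearly tables cannot show waning.** They can. Failures within an interval count until resumption, and resumption is optional (Protocol 6.5.1); see Step 5.
- **That every other durability endpoint keeps failures in.** Percentage without bleeds also excludes data after resumption (SAP 3.2.9), and FVIII by visit is not imputed for participants who leave for reasons other than lack of efficacy without resuming.
- **That the rise to 13.5 is a forecast.** It is mostly 35 times the share resumed, and that share is assumed.

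**Conclusion.** The point holds in a limited form. The yearly Total and Treated ABR tables estimate bleeding among participants not on prophylaxis, not durability in all who were dosed. They can understate waning when loss of effect leads promptly to resumption. The direction is robust under steady failure with prompt resumption; the size rests on failure rates, lags and bleed rates that the documents do not give. These are supplementary analyses without noninferiority or superiority tests and outside the gatekeeping sequence, so the primary conclusion and type I error are unaffected. The change is worth making because durability is a stated objective and no planned yearly ABR analysis retains failures.

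**What to change.** In SAP 6.1.1.2 and Appendix 2:

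1. Add a yearly-interval Total ABR analysis that applies the existing Table 10 rule (35 after resumption, including resumers who later discontinue), so that resumers stay in every later interval. Present 35 as a penalty value, not an observed rate.
2. Label the existing yearly Total and Treated ABR tables 'participants not on prophylaxis', and print beside each interval the cumulative numbers resumed and discontinued. Discontinuations without prior resumption stay unimputed and appear as a count.
3. Optionally, for Total ABR only, add a descriptive run on bleeds observed after resumption. Protocol 8.1.1 supports this: "Bleeds and non-prophylactic infusions (eg, on-demand and preventative) should continue to be reported throughout the course of the study". State that it includes the effect of resumed prophylaxis. It is not suited to Treated ABR: resumed prophylaxis infusions need not be entered in the eDiary after Week 78, while SAP Table 6 requires an infusion within 72 hours, for whatever reason, before a bleed counts as treated.
4. Reconcile the population labels (Efficacy in 6.1.1.2, Efficacy / Dosed in Appendix 2) and the 'same as above' entries for cumulative intervals, which literally carry over an exclusion written for yearly intervals.

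The cost is SAP wording and one or two extra runs of an existing model, with no new data collection. The downside for the sponsor is less favourable yearly ABR figures.
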